- *Research Repositories:* If the purpose of this submission is to establish a Research Repository (bank, registry) and the material you plan to collect is already available from a commercial supplier, clinical lab, or established IRB approved research repository, provide scientific justification for establishing an additional repository collecting duplicate material. Describe the repository design and operating procedures. For relevant information to include, see the [UK Research Biospecimen Bank Guidance](#) or the [UK Research Registry Guidance](#).

This study will use a within- and between-subjects, placebo-controlled, single-blind design in a sample of female (N=30) and male (N=30) young adult heavy drinkers. Subjects will attend four fMRI sessions (two in the early follicular phase and two in the mid-luteal

phase for women, and at matched intervals for men) in which they perform the stop signal task and a resting state undergoing either IV alcohol (60mg%) or saline infusion (placebo). Alcohol and saline sessions within each phase will be separated by 24-48 hours. Dose and phase order will be counter-balanced. Blood samples will be collected at baseline and during infusion to assess levels of estradiol, progesterone, and testosterone. The primary outcome measure will be brain activation during response inhibition.

Attachments

Subject Recruitment Methods & Advertising

Describe how the study team will identify and recruit subjects. Please consider the following items and provide additional information as needed so that the IRB can follow each step of the recruitment process.

- How will the study team identify potential participants?
- Who will first contact the potential subjects, and how?
- Will you use advertisements? If so, how will you distribute those?
- How and where will the research team meet with potential participants?
- If applicable, describe proposed outreach programs for recruiting women, minorities, or disparate populations.
- How will minimize undue influence in recruitment?
- Attach copies of all recruiting and advertising materials (emails, verbal scripts, flyers, posts, messages, etc.).

For additional information on recruiting and advertising:

- [IRB Application Instructions - Advertisements](#)
- [PI Guide to Identification and Recruitment of Human Subjects for Research](#)

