Determination of menstrual cycle phase. Women will complete a guided calendar-based interview to determine average menstrual cycle length and to estimate the onset of next menses (Roche and King 2015). Women will be randomly assigned to start in either the early follicular (2-7 days following the onset of menses) or the mid-luteal (5-10 days following ovulation) phase. Blood samples collected during each session will be used to retrospectively confirm that the targeted menstrual cycle phase was achieved. Ovulation will be confirmed by at-home urinary luteinizing hormone (LH) assays. Beginning on day 7 of their cycle, participants will complete the at-home LH assays every day, until a positive test is confirmed. They will be provided with small (2oz) cups and lids, as well as 20 LH tests. Each morning, they will use the cups to collect a small sample of urine. They will place the LH test (a short, paper stick) into the urine sample for 3 seconds, and then lie the test flat on the cup lid. Three minutes later, they will take a picture of the test and send it via text message to the Research Assistant. The RA will confirm whether the test is positive or negative. If negative, the RA will ask the participant to test again the next day, and if positive, the RA will inform the participant that she can stop the LH tests.

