**Attachments**

Attach Type	File Name
Study Drug Form	Ethanol_Side Effects, Dosages, Treatment, Interactions, Warnings.pdf
Study Drug Form	Study.Drug.Form.pdf
Study Drug Form	Alcohol_monograph.pdf
Study Drug Form	CofA Lot# 01RM1504A Ethanol.pdf
Study Drug Form	Ethanol_Label_Primary.pdf

Statistical Analysis Plan. *Statistical Analysis of Brain Activation:* The measures of brain activation during response inhibition (BARI) are activation in frontal ROIs (e.g., DLPFC, IFC, ACC, pre-SMA, SMA, and pre-motor cortex), as measured by BOLD % signal change, examined during response inhibition [StopInh>Go]. We will first check that men and women are matched on demographics and drug and alcohol use, and confirm that the [StopInh>Go] contrast activated the inhibitory network circuitry.

Statistical Analysis of Brain Activation: We will perform regression analyses in SPM12 to assess the degree to which baseline hormone levels predict change in BARI following alcohol compared to saline [StopInh>Go, Saline>Alcohol]. We hypothesize that greater baseline E2 will predict less activation following alcohol compared to saline. We will conduct a between-subjects t test to compare men and women on the StopInh>Go, Saline>Alcohol contrast. We hypothesize that alcohol effects on BARI will be greater in women compared to men. Finally, we will calculate change scores (alcohol minus baseline) for hormone levels, and perform regression analyses to predict [StopInh>Go, Saline>Alcohol] from change in hormone levels. We hypothesize that greater alcohol-induced increase in E2 will predict greater decrease in activation following alcohol.

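### The order factors created by the counter-balancing are not carried into the sex comparison or the two hormone regressions

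*Combined protocol and SAP*

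**What the plan says.** The Study Design section describes a within- and between-subjects comparison "in a sample of female (N=30) and male (N=30) young adult heavy drinkers". It continues: "Subjects will attend four fMRI sessions (two in the early follicular phase and two in the mid-luteal" phase for women, with matched intervals for men. On timing, "Alcohol and saline sessions within each phase will be separated by 24-48 hours", and on order, "Dose and phase order will be counter-balanced".

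Research Procedures (Determination of menstrual cycle phase) adds: "Women will be randomly assigned to start in either the early follicular" or the mid-luteal phase. No matching rule is given for men.

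The Statistical Analysis Plan names three inferential analyses of the saline-versus-alcohol contrast:

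- Baseline hormones: the investigators will "perform regression analyses in SPM12 to assess the degree to which baseline hormone levels predict change in BARI".
- Sex: "We will conduct a between-subjects t test to compare men and women on the StopInh>Go, Saline>Alcohol contrast".
- Hormone change: they will "perform regression analyses to predict [StopInh>Go, Saline>Alcohol] from change in hormone levels".

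None mentions order, session or period. The Data Monitoring Plan adds only that general linear model and regression methods in SPM and SPSS will be used. The documents do not give the dose sequences over the four sessions. Nor do they say whether balancing is done within each sex, whether the contrast is averaged over the two phases, or how a missing session is handled.

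**The concern.** Participants repeat the stop signal task in four scans. Familiarity with the task or habituation to the scanner could shift activation between an earlier and a later session. Counter-balancing makes such a shift cancel on average between alcohol and saline. It does not remove the shift from each person's own contrast, where it adds or subtracts according to which infusion came first. The design therefore creates a known, recorded source of variation, and the planned models leave it in the residual.

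Two things are at stake. One is power for Aim 4 (the sex difference) and for the hormone regressions. The other is protection of the sex contrast if the men and women finally analysed have different mixes of dose order.

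**Working it through.** **Inputs from the documents.** 30 women and 30 men; four sessions; dose and phase order counter-balanced. There is no power calculation to reproduce.

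**Assumptions.** Two-sided alpha 0.05; the SD of the per-person contrast, apart from order, is 1; dose order is split 15/15 in each sex; the later-minus-earlier session shift is π, in units of that SD. The documents give no value for π, so a range is shown. The benchmark d = 0.74 is the sex difference that 30 per sex detects with 80% power by t test.

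**Model.** Let D be saline minus alcohol. D = δ + π + e if alcohol came first, and D = δ − π + e if saline came first.

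**When π cancels.** This depends on the unstated sequences. Take a linear trend over sessions 1 to 4, with the contrast averaged over phases.

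- Order A-S-S-A: saline mean (2+3)/2 = 2.5, alcohol mean (1+4)/2 = 2.5. The trend cancels.
- Order A-S-A-S: saline mean (2+4)/2 = 3, alcohol mean (1+3)/2 = 2. One step of trend remains.

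**Power when π does not cancel and orders are balanced.** The true SE of the sex difference is √(2/30) = 0.258 for every π, because the ±π terms sum to zero within each sex. The unadjusted residual sum of squares has 58 df and noncentrality 60π², so the typical estimated SE is √[(58 + 60π²)/58 × 2/30]. At π = 0.5 this is √(73/58) × 0.258 = 0.290. Simulation from this model at d = 0.74 gives:

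| π | Estimated SE | Type I error, unadjusted | Power, unadjusted | Power with order term |
|---|---|---|---|---|
| 0 | 0.258 | 0.05 | 80% | 80% |
| 0.25 | 0.266 | 0.04 | 79% | 80% |
| 0.3 | 0.270 | 0.04 | 78% | 80% |
| 0.5 | 0.290 | 0.03 | 73% | 80% |
| 0.8 | 0.333 | 0.01 | 61% | 80% |

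**Bias.** With p the alcohol-first share among those analysed, the bias in the sex contrast is 2π(p_women − p_men). Cells below are alcohol-first/saline-first.

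- 12/12 v 15/15, or 15/9 in both sexes: zero.
- 15/13 v 13/15: 2π(15/28 − 13/28) = 0.14π.
- 15/9 v 15/15: 2π(15/24 − 15/30) = 0.25π, or 0.125 SD at π = 0.5.
- 9/15 v 15/15: −0.25π. At π = 0.5 and d = 0.74, power is 51% unadjusted and 75% with the order term.
- 15/9 v 9/15, a severe case: 0.50π. At π = 0.5, type I error is 0.092 unadjusted and 0.05 with the order term.

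With the order term the bias is zero in every case.

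**The case against.** The case for leaving the plan alone has real weight.

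- **π may be small.** The outcome is a within-session contrast of correct stops against correct go trials, so shifts common to both trial types drop out. The stop delay adapts to 50% success, and practice is given at orientation and before each scan. At π = 0.25 the power cost is under two points. All this stands, but none of it shows that π is zero, and practice rounds do not deal with scanner habituation.
- **The sequences may already cancel a trend.** This stands as a possibility. The documents do not settle it.
- **The SAP is a short summary, and a general linear model allows covariates.** A reader might infer that order was deliberately excluded. The text is only silent. Even so, a between-subjects t test as named has no place for a covariate.

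Some stronger readings are tempting, and the documents do not support them.

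- **Lost sample.** Dividing d by √(1 + π²) gives powers of 77%, 71% and 59% at π = 0.3, 0.5 and 0.8, and implies an effective sample loss of 8%, 20% and 39%. That treats order as random noise. Under balanced orders the sex estimate loses no precision; only its estimated SE is inflated.
- **Bias from unequal drop-out as such.** A different drop-out rate by sex is not enough, because the order mix must differ. If each cell starts at 15, drop-out cannot produce, for example, 17/11 v 12/16 (a bias of 0.36π). That split would need order not to have been balanced within sex, which the documents neither state nor exclude.
- **All aims affected.** The SAP gives no analysis of cycle phase for Aim 2, so there is no standard error there to inflate.

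A differing order mix is nonetheless possible. Exclusion for a positive pregnancy test and retrospective confirmation of cycle phase apply only to women, and no replacement rule is given. Nothing in the documents links loss of data to dose order.

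**Conclusion.** The omission is real in all three planned analyses of the contrast. With complete, balanced data it does not bias the sex comparison. It makes the t test conservative, with power at d = 0.74 falling from 80% to about 79%, 78%, 73% or 61% for π of 0.25, 0.3, 0.5 or 0.8. Bias of 0.14π to 0.25π appears in the moderate examples where the order mix differs by sex, and is zero otherwise.

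These sizes rest on an assumed π, on balanced starting cells, and on a session effect that does not cancel within person. The hormone regressions leave the same shift in their residual; no separate power figure is given for them. A reader should not conclude that the sex result will be biased, or that the design is unsound. This is a nearly free improvement that is best specified before the data are seen.

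**What to change.** - Replace the plain t test with a linear model of the saline-minus-alcohol contrast on sex, dose order and phase order, each order factor coded ±0.5. With one dose order per person, the dose-order coefficient estimates 2π and should be reported. Alternatively, use a session-level mixed model with session number as a fixed effect.
- Add the same order terms to both hormone regressions.
- List the four-session sequences, say whether they are balanced within each sex, define the equivalent of phase order for men, and state whether the contrast is averaged over phases. If dose order can change between phases, code it by phase or use the session-level model.
- Report the order mix by sex among those analysed.

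The cost is one or two degrees of freedom out of 58 in the sex comparison and a few sentences in the SAP. No new data are needed, because the order of sessions is known for each participant.

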Once the scanning session is complete, the nurse will remove the intravenous catheters and the subject will be escorted back to Kastle Hall. We will obtain a breath alcohol sample and subjects will be allowed to leave the laboratory when BrAC is below 20mg% (NIAAA guidelines). If subjects are not able to arrange alternative transportation, we will provide transportation home. After the final imaging session, participants will attend a debriefing session, either in person or over the phone, in which the purpose of the study and the infusions they received will be told to them, and they can ask questions about the study.

Attachments

Data Collection & Research Materials

In this section, please provide the following:

- Describe all sources or methods for obtaining research materials about or from living individuals (such as specimens, records, surveys, interviews, participant observation, etc.), and explain why this information is needed to conduct the study.
- For each source or method described, please list or attach all data to be collected (such as genetic information, interview scripts, survey tools, data collection forms for existing data, etc.).
- If you will conduct a record or chart review, list the beginning and end dates of the records you will view.

The research material consists of subjects' questionnaire scores, diagnostic test scores, urine analyses for drug metabolites and urine human chorionic gonadotrophin (pregnancy), fMRI data (BOLD, CBF), hormonal assays (estradiol, progesterone, testosterone), behavioral performance on the stop signal task, and subjective reports (BAES, DEQ). Drug metabolites tested include: amphetamine and amphetamine salts (e.g., methylphenidate), barbiturates, benzodiazepines, cocaine, opiates, and tetrahydrocannabinol. (No archival records or other data will be used). Authentication of drug and pregnancy tests is assured by purchase only from reputable commercial dealers who must adhere and document specific quality standards. The Timeline Follow-back (TLFB) and Alcohol Use Disorders Identification Test (AUDIT) will be used to provide valid and reliable assessments of drinking habits and problems, including typical frequency and quantity of alcohol consumption (number of standard drinks). These measures will be used to confirm that all participants meet criteria for heavy drinking (i.e., 10-30 drinks per week and at least two binge episodes (4/5 drinks or more for women/men in two hours) in a 30 day period on the TLFB and a score of 8 or above on the AUDIT). Trait impulsivity measures will also be assessed, including the UPPS-P and BIS-11.

Dependent Measures: Subjects will complete the following measures during each brain imaging session.

Stop Signal Task: While in the scanner, participants will complete three runs of the stop signal task, adapted and validated for use in fMRI (Kareken et al. 2013). Participants are instructed to respond as quickly as possible when a 'go' target appears (left or right arrow) by hitting the corresponding left or right button on the MRI-compatible keypad. They are also instructed to inhibit that response when a 'stop' signal (a red vertical arrow) occasionally occurs. Each run consists of 80 'go' trials and 40 'stop' trials. The duration of the delay to presentation of the stop signal following the go signal is adjusted until the participant is able to successfully inhibit the response on 50% of trials. The final mean delay of the stop signal, based on this 50% success rate criterion, is subtracted from the mean go reaction time, providing the stop signal reaction time (SSRT), which is the behavioral measure of response inhibition. The BOLD contrast of interest will be activation during correct inhibition trials compared to correct go trials [StopInh>Go].

Hormone assays: Serum assays of estradiol, progesterone, and testosterone will be analyzed by the CCTS Biomarker Analysis Lab.

Subjective Alcohol Effects: Subjective reports of mood and drug effects will be assessed using the BAES (a 14-item scale that measures stimulation and sedation) and the DEQ (a 100 mm visual analogue scale that measures the following: feel substance, like substance, and want more of the substance). Both scales have well-documented validity.

Attachments

Attach Type	File Name
DataCollection	UPPS-P-PaperCopy.doc
DataCollection	AUDIT.docx
DataCollection	BAESPaperCopy.doc
DataCollection	DEQ paper version.doc
DataCollection	TLFB.docx
DataCollection	BIS questionnaire.pdf

Resources

Describe the availability of the resources and adequacy of the facilities that you will use to perform the research. Such resources may include:

- Staffing and personnel, in terms of availability, number, expertise, and experience;
- Computer or other technological resources, mobile or otherwise, required or created during the conduct of the research;
- Psychological, social, or medical services, including equipment needed to protect subjects, medical monitoring, ancillary care, or counseling or social support services that may be required because of research participation;
- Resources for communication with subjects, such as language translation/interpretation services.

All of the equipment and space needed to conduct this study is available in Kastle Hall, the MRISC, and the CRU. Within Kastle Hall, there is a private room for testing volunteers, including a desktop computer. The MRISC houses a Siemens Prisma 3T scanner, along

with an AVOTEC SL-6011 LCD projection system used with Psychology Software Tools Inc. visual presentation system; MRA, Inc. 10 channel, fiber optic, patient response system with trigger interface and visual/auditory patient monitoring; Current Designs, Inc. patient response Interface Unit with 12 fiber optic cables and an MRI-compatible handheld, trackball mouse; Medrad, Inc. SHS200 Power Injector; InVivo Research, Inc. Press 3160 MRI compatible physiological monitoring unit with a pulse oximeter, blood pressure cuff, intravascular blood pressure, ECG, respiration and CO₂ monitoring. The CRU is an NIH-funded research unit, and a fully equipped and professionally staffed medical unit. The CRU provides support for nursing staff. I will utilize the CRU for several key aspects of this project, including drawing blood samples for hormonal assays, inserting the IV catheters and tubing for IV alcohol and saline administration, and administering the alcohol and saline infusions using pumps.

Potential Risks & Benefits

Risks

- Describe any potential risks – including physical, psychological, social, legal, ability to re-identify subjects, or other risks. Assess the seriousness and likelihood of each risk.
- Which risks may affect a subject's willingness to participate in the study?
- Describe likely adverse effects of drugs, biologics, devices or procedures participants may encounter while in the study.
- *Qualitative research* - describe ethical issues that could arise while conducting research in the field and strategies you may use to handle those situations.
- Describe any steps to mitigate these risks.

Benefits

- Describe potential direct benefits to study participants – including diagnostic or therapeutic, physical, psychological or emotional, learning benefits. This cannot include incentives or payments.
- State if there are no direct benefits.
- Describe potential benefits to society and/or general knowledge to be gained.

Describe why potential benefits are reasonable in relation to potential risks. If applicable, justify why risks to vulnerable subjects are reasonable to potential benefits.

The potential risks in this study are minimal and involve risks of 1) confidentiality; 2) the fMRI procedure; 3) insertion of intravenous catheters and needles (for IV alcohol administration and blood draws); 4) administration of alcohol; and 5) pregnancy testing.

1. Confidentiality: Laboratory personnel strictly maintain confidentiality, and records are kept in a secure location. However, there is a risk that a volunteer's Protected Health Information (PHI) may be seen by others. PHI is considered individually identifiable health information transmitted or maintained in any form (i.e., electronic means, on paper, or through oral communication) that relates to the past, present, or future physical or mental health conditions of an individual that may be used or disclosed. The following PHI will be collected as part of this project: name, address, telephone number, Social Security number, dates (birth, admission, discharge), medical record numbers, mental and physical health history, drug use history, results from mental and physical health screening, and data from experimental measures. All data will be coded by participant number only and any personal identifiers linking participants to their reports on questionnaires will be detached and destroyed as soon as participation is completed or disqualification occurs.

2. fMRI procedure: fMRI is a non-invasive procedure that is widely used and safe. Potential risks such as static magnetic field, radio-frequency field, magnetic field gradients, and acoustic noise are rarely dangerous or life-threatening. The risks of the study are extremely small when exclusion criteria are observed and are outweighed by the large benefits of these studies to clinical and neuroscience research. Subjects will be asked questions about claustrophobia and the presence of metal in their body to make sure that the MRI scan is safe. If they have implanted metal of any kind, they will not be scanned. For their safety, they will be asked to remove any metal in their clothing before the scan (for example, belts and rings). Subjects will be given noise dampening head phones to reduce the discomfort due to the noise of the machines. Subjects are asked to report any discomfort immediately. They may discontinue the scan at any time if they are too anxious to continue, by communicating with the scanning operator that they would like to end the session. Additional minor or rare risks include: i) discomfort from lying still for 1 hour; ii) fast imaging sequences may potentially induce peripheral nerve stimulation (PNS) that may cause mild discomfort but is not harmful to participants; iii) anxiety or panic attack caused by close confinement in the scanner; iv) the MRI may reveal a minor or significant lesion in the brain (e.g., tumor) previously unknown to the subject. The CRC nurse and PI and also the Study Physician will be available and/or present during the fMRI scans in order to evaluate the emergence of any anxiety/panic attack, elevated levels of anxiety, or emotional discomfort during the procedure.

3. Insertion of needles/catheters: Some risks are associated with the insertion of intravenous catheters. These include bruising and pain at the site of the needle insertion, and a small risk of infection. A trained CRU nurse will perform blood draws and catheter insertion to minimize pain and standard sterilization techniques and other routine precautions will be utilized in order to minimize the risk of needle-site infections.

4. Intravenous administration of alcohol: The possible adverse effects of alcohol include pain at the injection site, disorientation, or sedation. Nausea and/or vomiting are extremely unlikely given the moderate dose administered. No serious adverse effects have been reported in healthy men and women following intravenous administration of a 6% alcohol solution (Blekher et al. 2002; Davidson et al. 1997; Ray and Hutchinson 2004; Yoder et al. 2005). We have successfully administered a higher dose (80mg%) than that proposed here (60mg%) intravenously both in and out of the scanner (Weafer et al. 2018).

5. Pregnancy testing. There is a risk of psychological discomfort from exposure to a pregnancy test or the upset that might result from an unexpected non-negative outcome. These tests do, of course, require the participant's consent and cooperation, and all potential female participants are given advance notice of this test during initial phone contact. The PI's standard operation procedures will call for the exclusive use of a trained Research Assistant (RA) to give instructions, process the samples, and report the results to participants individually. The RA will advise participants of the conclusiveness of negative results and also stress the ambiguity of non-negative outcomes. The RA will explain that rather than repeating non-negative tests to try to rule out a possible false-positive, any

ambiguous result is grounds for disqualification. The assistant will also immediately offer specific advice about what precise follow-up testing and provide information about how to get counseling if desired.

The risks to subjects are justified by the knowledge to be gained regarding sex-specific behavioral and brain-mediated processes related to alcohol use. Knowledge about sex-specific risk factors for alcohol abuse will inform our understanding of the development and treatment of drug and alcohol use disorders in men and women. Also, participants in the research derive considerable educational benefit from their participation. Subjects are genuinely interested in studies of alcohol and have many questions about how the drug may affect them. The feedback to participants includes written educational information about blood alcohol levels and the risks of impairment likely to result from drinking various amounts of alcohol. Participants in our studies often comment that this information is extremely helpful in judging the safety of their drinking practices and deciding about activities, such as driving after drinking. Given the potential educational benefits that subjects derive from participating in this research, the minimal risk to subjects in this research is reasonable.

Available Alternative Opportunities/Treatments

Describe alternative treatments or opportunities that might be available to those who choose not to participate in the study, and which offer the subject equal or greater advantages. If applicable, this should include a discussion of the current standard of care treatment(s).

There are no alternative treatments.

[Back to Top](#)

Records, Privacy, and Confidentiality

Specify where the data and/or specimens will be stored and how the researcher will ensure the privacy and confidentiality of both. Specify who will have access to the data/specimens and why they need access.

Describe how data will be managed after the study is complete:

- If data/specimens will be maintained, specify whether identifiers will be removed from the maintained information/material.
- If identifiers will not be removed, provide justification for retaining them and describe how you will protect confidentiality.
- If the data/specimens will be destroyed, verify that this will not violate [retention policies](#) and will adhere to applicable facility requirements.

If this study will use de-identified data from another source, describe what measures will be taken to ensure that subject identifiers are not given to the investigator.

If applicable, describe procedures for sharing data/specimens with collaborators not affiliated with UK.

For additional considerations:

[Return of Research Results or Incidental Research Findings](#)

[HIPAA policies](#)

[FERPA policies](#)

[Procedures for Transfer agreements](#)

[Information regarding multi-site studies](#)

[NIH Genomic Data Sharing \(GDS\) Policy](#)

[Digital Data](#)

All research materials obtained from participants will be collected directly from them at the time of recruitment and participation. The research material consists of subjects' questionnaire scores, fMRI data (BOLD, CBF), hormonal assays (estradiol, progesterone, testosterone), behavioral performance on the stop signal task, and subjective reports (BAES, DEQ). No archival records or other data will be used. All data will be coded by participant numbers and any personal identifiers linking participants to their reports on questionnaires and computer tests will be maintained in a separate location by the PI. The data will then be transferred to computer files with all individual identifiers removed. All data will be stored in coded files and locked in the laboratory area. All information will be in the form of numerical data and used for research purposes only. Results will be reported only for groups, and no single individual will be identified. Personal identifiers, such as names, will be removed from the subjects' data records. Urine samples will be collected at screening, prior to a subject's participation in the experimental protocol. These urine samples will be tested for the presence of a full range of drugs of abuse. Drug urine screens and urine pregnancy tests will also be conducted daily during the experimental protocol. Expired air samples will also be taken at these times to detect the presence of recent alcohol consumption. Other research materials obtained from the volunteers include demographic information, mental and physical health screening information, experimental data, and non-intrusive staff observations. Experimental data include the stop signal task measures, fMRI BOLD/CBF data, hormonal assays, and self-reported responses on questionnaires.

Files will not contain the name of the volunteer. Instead, each volunteer will be assigned a unique identifying number. All written documents will be stored in locked cabinets in the PI's office (Kastle Hall Room 205). All data will be retained for a period of at least six years after the end of the IRB approval period. Key access will be limited to immediate laboratory personnel. Electronic information will reside on a stand-alone, password-protected computer.

To protect or minimize any possible risks, we will follow these procedures:

1. Subjects will be carefully screened to exclude those who are physically or psychiatrically at risk.
2. The study will be conducted in the MRISC and the CRU (both of which are located in the hospital), where emergency assistance, including the Study Physician ([name]), is close at hand. [name] will provide medical consultation for the project and 24 hour on-call support from the Psychiatry Department. All laboratory technicians will have completed the training course on Human Subjects

Protection and will be CPR and first-aid certified.

3. A technician or nurse is present during all sessions.

4. Subjects agree not to take any drugs for 24 hours before the sessions and compliance is monitored by breathalyzer and urine tests.

5. Subjects will remain in the laboratory until their BrACs have fallen below 20mg% (per NIAAA guidelines), and they will be provided with transportation home if needed.

6. Subject files containing confidential information will be maintained in a locked cabinet in the PI's office (Kastle Hall Room 205). Only personnel directly connected with the study have access to this information, and these individuals are instructed in the importance and procedures for maintaining confidentiality.

7. Data collected in the study are identified by subject codes only, and no data will be published in a form by which the subject can be identified.

8. MRI Scanning: Necessary precautions for safety for magnetic exposure will be taken and ensured in each subject and each will be screened for MRI safety with a standard MR Safety form. Any individuals who have potential MRI risks, such as pacemakers, surgical clips, metallic surgical devices, and/or other irremovable ferrous-containing materials, will be excluded. Minor risk of discomfort due to lying still for 1 hour will be minimized by custom pads and pillows to make the subject as comfortable as possible. Subjects will be constantly monitored for any side effects and will be treated appropriately by the available physicians and nurses. Earplugs may be used to reduce discomfort due to noise. The study may be aborted if the subject has any discomfort. The safety of the subjects will be continually monitored. Regarding the potential for PNS, the MRI machine is operated within FDA guidelines so the potential for PNS is low.

Discovery and disclosure of incidental finding or abnormality on MRI scans: First, all subjects will be instructed in their formal consent process about the potential risks of discovering an incidental finding or abnormality on their MRI scan. Second, if an abnormality is found in a subject's MRI scan, the Study Physician will contact the subject and refer the patient for medical follow-up for the problem if the subject requests, including referral to a primary care doctor. If a subject has a primary care doctor, the Study Physician will contact the subject's doctor, at the request and with the permission of the subject, to inform him/her of the finding on the MRI scan and to help him/her to get the subject the appropriate follow-up. The decision as to whether to proceed with further examination or treatment lies solely with the subject and his/her primary care physician.

9. Alcohol Infusions: Subjects will be monitored carefully by the nurse and PI during infusions. Infusions and scans will be terminated and the subject removed from the scanner immediately if they report feeling nauseated. Subjects will fast for the 2 hours before scanning begins to minimize the possibility of aspiration of stomach contents. Additionally, the subject's head will be restrained only by a conformal pillow while in the scanner; they will be able to lift their heads at any time. Infusion solution will be prepared by the University of Kentucky Hospital Pharmacy Investigational Drug Service to ensure that the concentration of the infusate is not any higher than 6% alcohol, in order to reduce the risk of pain at the injection site. Infusion solutions will also be warmed using instant heat packs. The calculated pump rate will be close to the maximum rate of the pump and therefore accidental overdose due to the use of higher than calculated pump rates will be unlikely. Alarmed timers will be used by the nurse and PI to monitor the length of the infusion. All calculations will be double checked with the Senior MRI Research Technologist. We will exclude subjects who have not previously consumed alcohol and those who report less than regular moderate to heavy alcohol consumption.

10. A list of counseling and substance abuse treatment referrals will be provided to all participants. This referral will include psychological services such as The Harris Center at [contact].

11. The study will employ a pre-screening eligibility survey to determine if a volunteer meets basic inclusion/exclusion criteria. We will build and administer the eligibility survey on UK's REDCap which provides HIPAA compliant storage on UK servers and encrypted transmission of survey responses. The portable devices do not download the data, it is directly stored into the secure web-based connection ([https](https://)) behind the firewall. All files are password protected once entered into the system. All project data is stored and hosted locally.

UK IRB policies state that IRB-related research records must be retained for a minimum of 6 years after study closure. Do you confirm that you will retain all IRB-related records for a minimum of 6 years after study closure?

Yes No

Payment

Describe the incentives (monetary or other) being offered to subjects for their participation. If monetary compensation is offered, indicate the amount and describe the terms and schedule of payment. Please review [this guidance](#) for more information on payments to subjects, including restrictions and expectations.

Participants will receive \$75 for each brain imaging session attended, plus a \$100 completion bonus, for a total of \$400.

Costs to Subjects

Include a list of services and/or tests that will not be paid for by the sponsor and/or the study (e.g., MRI, HIV). Keep in mind that a subject will not know what is "standard" – and thus not covered by the sponsor/study – unless you tell them.

There are no anticipated costs to subjects.

Data and Safety Monitoring

The IRB requires review and approval of data and safety monitoring plans for greater than minimal risk research or NIH-funded/FDA-regulated clinical investigations.

- If you are conducting greater than minimal risk research, or your clinical investigation is NIH-funded, describe the Monitoring Plan (DSMP). [Click here for additional guidance on developing a Data and Safety Monitoring Plan](#).
- If this is a non-sponsored investigator-initiated protocol considered greater than minimal risk research, and if you are planning on using a Data and Safety Monitoring Board (DSMB) as part of your DSMP, [click here for additional guidance](#) for information to include with your IRB application.

1

The data and safety monitoring plan for this study follows the NIAAA guidelines for the administration of alcohol. The PI will be responsible for monitoring the safety and efficacy of the proposed study, executing the DSMP, and complying with the reporting requirements. The PI will be assisted by [name], the Study Physician, in the event that medical consultations are needed. A summary of the DSM report will be included in the annual progress report to NIAAA. The subjects' sociodemographic characteristics, expected versus actual recruitment rates, summary of AEs and SAEs, and any actions or changes with respect to the protocol will be included in this report.

